6.2.4 Completion/Final Evaluation

We will repeat a final EHR review for evidence of documented conversation related to these medications. In addition, we will review the active medications to determine the primary outcome of changes to the CNS-active medication regimen.

Additionally, we will conduct informant interviews with 10 primary care clinicians across intervention clinics from U-M and HFHS. The purpose of these interviews will be to explore potential barriers with experts and will explore whether:

- PLWD discussed receiving the tool with the clinician;
- Clinician perception of whether the tool motivated:
 - discussion related to prescribing that might not have occurred otherwise;
 - prescribing changes that might not have occurred otherwise;

- Clinician suggestions for modifications to the tool;
- Clinician suggestions regarding their perceived barriers or facilitators to improving the appropriateness of CNS-active prescribing, e.g.:
 - Clinical uncertainty regarding which medications to address;
 - Lack of access to clinical pharmacists to facilitate medication changes;
 - Lack of psychosocial resources for the PLWD-CP dyad.

7 **SAFETY ASSESSMENTS**

7.1 **Specification of Safety Parameters**

n/a

7.2 **Methods and Timing for Assessing, Recording, and Analyzing Safety Parameters**

The intervention is presenting education, which has a benign safety profile. Should the participants, in consultation with their clinician, choose to make medication changes, then participants should be at *lower* risk of adverse events by minimizing the burden of these medications. In a recent study of deprescribing among PLWD (of any, not limited by medication class), there was no difference in hospitalization or mortality rates in intervention groups, and review of records did not “reveal any pattern of adverse drug withdrawal events associated with the intervention.”¹⁷ In the original EMPOWER intervention (deprescribing of sedative-hypnotics), “no major adverse effects requiring hospitalization were reported.”¹⁵

Study participants will be identified using the EHRs and the intervention will consist of mailed materials to the participant—otherwise, the study team has no contact with study participants. Therefore, any potential adverse event reporting will come to the research team through clinics from which patients are identified. In the event of clinic staff notifying the study team of a serious and unexpected adverse event, the PI will follow the required reporting protocols detailed below.

7.3 **Adverse Events and Serious Adverse Events**

AE Definition: AE is any untoward or unfavorable medical occurrence in a human study participant, including any abnormal sign (e.g. abnormal physical exam or laboratory finding), symptom, or disease, temporally associated with the participants’ involvement in the research, whether or not considered related to participation in the research.

SAE Definition: SAEs consist of any adverse event that results in death; is life threatening or places the participant at immediate risk of death from the event as it occurred; requires or prolongs hospitalization; causes persistent or significant disability or incapacity; is another condition which investigators judge to represent significant hazards.

Unanticipated Problem (UP) Definition: any incident, experience, or outcome that meets all of the following criteria:

- unexpected, in terms of nature, severity, or frequency, given (a) the research procedures that are described in the protocol-related documents, such as the IRB-approved research protocol and informed consent document; and (b) the characteristics of the study population;
- related or possibly related to participation in the research;
- suggests that the research places participants or others at a greater risk of harm (including physical, psychological, economic, or social harm) than was previously known or recognized.

AEs for this study include:

AEs for this study include a PLWD making medication changes without first consulting with a treating clinician. This may be revealed during the 2-month and 4-month chart reviews or by the prescribing clinician. Given risks associated with usual care (e.g., risk of respiratory suppression and death from common psychotropic-opioid combinations), while we will consider self-directed medication change an AE, in fact PLWD risk of medication-related adverse events would likely be lower than the risk from usual care (i.e., without change). Overall, we consider the potential for AEs to be low.

SAEs for this study include:

SAEs are not related nor anticipated as a result of this study. The study activities pose minimal risks. Death or hospitalization can reasonably be expected considering the study population includes persons living with dementia and those experiencing CNS polyRx. However, the study activities will not contribute to the death of participants; in fact, reducing burden of CNS-active medication should lower the risk of death. Prior deprescribing intervention studies in older adults demonstrate no impact on hospitalization or death.¹⁷¹⁵

7.3.1 Reporting Procedures

Severity of Event

All data and safety monitoring reporting will classify SAEs and AEs as to their severity, expectedness, and potential relatedness to the study intervention as per the definitions below:

Severity

- **Mild:** Awareness of signs or symptoms, but easily tolerated and are of minor irritant type causing no loss of time from normal activities. Symptoms do not require therapy or a medical evaluation; signs and symptoms are transient.
- **Moderate:** Events introduce a low level of inconvenience or concern to the participant and may interfere with daily activities, but are usually improved by simple therapeutic measures; moderate experiences may cause some interference with functioning
- **Severe:** Events interrupt the participant's normal daily activities and generally require systemic drug therapy or other treatment; they are usually incapacitating

Relationship To Study Intervention

Definitely Related: The adverse event is clearly related to the investigational agent/procedure – i.e. an event that follows a reasonable temporal sequence from administration of the study intervention, follows a known or expected response pattern to the suspected intervention, that is confirmed by improvement on stopping and reappearance of the event on repeated exposure and that could not be reasonably explained by the known characteristics of the subject's clinical state.

Possibly Related: An adverse event that follows a reasonable temporal sequence from administration of the study intervention follows a known or expected response pattern to the suspected intervention, but that could readily have been produced by a number of other factors.

Not Related: The adverse event is clearly not related to the investigational agent/procedure - i.e. another cause of the event is most plausible; and/or a clinically plausible temporal sequence is inconsistent with the onset of the event and the study intervention and/or a causal relationship is considered biologically implausible.

7.3.2 Follow-up for Adverse Events

Reporting Schedule:

- All adverse events that are serious (SAE) and unexpected (i.e., have not been previously reported for the study's intervention) will be reported to the IMPACT Collaboratory Regulatory and Data Team Leader ([name]), NIA IMPACT Collaboratory PO ([name]), and the IMPACT Collaboratory Safety Officer (SO) within 48 hours of the study's knowledge of SAE.
 - Only those adverse events that are serious (SAE), unexpected, and related to the intervention must also be reported to Advarra IRB. Unexpected and unrelated SAEs will be reported to Advarra IRB on a case-by-case basis if requested by the IMPACT Collaboratory Safety Officer (SO) or NIA IMPACT Collaboratory PO.
- All deaths will be reported to IMPACT Collaboratory Regulatory and Data Team Leader ([name]), NIA IMPACT Collaboratory PO ([name]), and the Safety Officer, [name] within 24 hours of study's knowledge of death.
 - Advarra IRB does not require the specific reporting of death outside of the SAE reporting requirement above, but they will be notified on a case-by-case basis if requested by the IMPACT Collaboratory Safety Officer (SO) or NIA IMPACT Collaboratory PO.
- All unanticipated problems (UPs) will be reported to the IMPACT Collaboratory Regulatory and Data Team Leader ([name]), Advarra IRB, NIA IMPACT Collaboratory PO ([name]), and the Safety Officer, [name] within 48 hours of the study's knowledge of the event.

- The summaries of all previously reported unexpected and related SAEs, deaths, and UPs, as well as all other SAEs and AEs will be reported to IMPACT Collaboratory Regulatory and Data Team Lead ([name]), Advarra IRB, NIA IMPACT Collaboratory PO ([name]), and the IMPACT Collaboratory Safety Officer, [name] at a minimum every 6 months, or at a frequency requested by the Safety Officer or NIA IMPACT Collaboratory PO.

7.4 Safety Monitoring

The NIA Guidelines on Data and Safety Monitoring generally require that a NIA-appointed Data and Safety Monitoring Board or Safety Officer monitor clinical trials. Please see the [Data and Safety Monitoring Guidelines](#).

8 INTERVENTION DISCONTINUATION

For this pragmatic intervention, there is no specific intervention discontinuation. The intervention consists of providing educational information on one occasion and it will be up to the dyad and clinician whether there are any resulting medication changes.

9 STATISTICAL CONSIDERATIONS

9.1 General Design Issues

For this nudge intervention, the primary clinical outcome will be change in the total standardized daily dosage (TSDD) of the medication classes contributing to CNS polyRx as measured in the EHR, from baseline to 4 months after sending the adapted intervention. We hypothesize a decline in the total standardized daily dosage (TSDD) following the nudge intervention. The presumed mechanism of the intervention is that the nudge educational tool will activate the dyad to discuss their current medication regimen with the prescribing clinician or a pharmacist. To determine whether the intervention has had this desired effect, as an implementation feasibility target, the team at each site will revisit intervention PLWD charts to complete an expedited chart review. We will complete initial reviews approximately two months after sending the tool and final review four months after sending the tool.

9.2 Sample Size and Randomization

Our goal of participants is a total of 120 PLWD (a total of 60 across 2 intervention clinics; 60 across 2 control clinics), after allowing for clinician opt-out. This will then allow us to obtain a reasonably precise estimate of the first feasibility outcome (i.e., documentation of a prescribing-related conversation in the EHR), allowing us to determine the number of clinics within each health care system needed for the future ePCT. We will also be able to estimate the lower limit of a 95% confidence interval around the implementation feasibility target (i.e., documented discussion regarding CNS polyRx) not to drop below the pre-determined target of 50%. With N=60 PLWD (i.e., the PLWD in the intervention clinics) and assuming 65% to 75% to show evidence of CNS-medication discussions, the lower limits of a 95% confidence interval for implementation

feasibility target will be 51.6% to 62.1%, respectively. Meeting the implementation feasibility target will allow us to proceed to a full ePCT.

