1 STUDY OBJECTIVES

1.1 Primary Objective

The primary clinical outcome will be change in the total standardized daily dosage (TSDD) of the medication classes contributing to CNS polyRx as measured in the EHR, from baseline to 4 months after sending the adapted intervention. We hypothesize that the TSDD of the medication classes contributing to CNS polyRx will decline from baseline to 4 months in participants receiving the nudge intervention (though this pilot study is not designed [or powered] to detect a statistically significant change).

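### Section 9.2 presents lower limits of 51.6% and 62.1% as what the trial will deliver, but the 50% criterion is met only about 56% of the time if the true rate is 65%

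*Combined protocol and SAP*

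**What the plan says.** All of this is in section 9.2 (Sample Size and Randomization) of the combined protocol and SAP.

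- The planned sample is "a total of 60 across 2 intervention clinics; 60 across 2 control clinics". The feasibility proportion uses the intervention half only: "With N=60 PLWD (i.e., the PLWD in the intervention clinics".
- The aim is that the lower 95% limit for documented discussion is "not to drop below the pre-determined target of 50" percent.
- The support offered is: "assuming 65% to 75% to show evidence of CNS-medication discussions, the lower limits of a 95% confidence interval" for the "feasibility target will be 51.6% to 62.1%, respectively".
- The consequence is: "Meeting the implementation feasibility target will allow us to proceed to a full ePCT".

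The section does not name the interval method or state any probability of meeting the target. It also does not say that the limits apply only when the observed proportion equals the assumed one.

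**The concern.** A lower confidence limit is computed from the observed count, and that count varies around its expectation. Putting the assumed rate in the place of the observed rate gives the limit for one possible result. It does not show that the limit will stay above 50% whenever the true rate lies in the assumed range. The section words its figures as what the limits will be, and as keeping clear of 50%, so a reader would take the design to be safe from 65% upwards.

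Section 9.2 ties this target to going on to the full trial. If the low end of the planning range falls on the pass/fail boundary, the sponsor and funder should know that before the result is seen.

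**Working it through.** **Inputs, all from section 9.2.** N = 60 intervention patients; assumed rate 65% to 75%; 95% confidence; target 50%; stated lower limits 51.6% and 62.1%; two intervention clinics, so about 30 patients each. The interval method and an intraclass correlation (ICC) are not given.

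**Step 1: reproduce the stated limits.** 65% of 60 is 39 and 75% of 60 is 45. The two-sided exact (Clopper-Pearson) lower limit for x events in n is the 2.5% quantile of a Beta(x, n − x + 1) distribution.

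- 39/60: Beta(39, 22) gives 51.60%.
- 45/60: Beta(45, 16) gives 62.14%.

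Both match. Other methods do not match both: Wald gives 52.9% and 64.0%, Wilson 52.4% and 62.8%, Jeffreys 52.5% and 63.1%, and a one-sided exact limit 53.6% and 64.2%. The two-sided exact interval is therefore inferred as the plan's method.

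**Step 2: find the count that meets the criterion.** With the same interval, 38/60 gives 49.9% and fails, while 39/60 gives 51.6% and passes. The criterion is at least 39 of 60. The expected count at a true rate of 65% is 0.65 × 60 = 39, exactly on the threshold.

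**Step 3: probability of meeting it.** With independent patients, X ~ Binomial(60, p), and the probability is P(X ≥ 39).

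| True rate p | P(X ≥ 39) |
|---|---|
| 65% | 0.559 |
| 70% | 0.838 |
| 75% | 0.970 |

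Solving P(X ≥ 39) = 0.80 gives p of about 69.2%; for 0.90, p is about 71.7%.

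**Step 4: sensitivity to the interval method.** Wilson, Wald, Jeffreys or Agresti-Coull limits move the threshold to 38/60. The probability is then 0.662 at 65%, 0.896 at 70% and 0.985 at 75%. A one-sided 95% limit moves it to 37/60, with 0.753 at 65%.

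**Step 5: sensitivity to N.** Under the exact rule N = 58 needs 37 (probability 0.63 at 65%) and N = 70 needs 44 (0.70 at 65%). A fixed count of 39 is right only if N is exactly 60.

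**Step 6: clustering, as an assumption.** Take an ICC of 0.02 to 0.05 and two clinics of 30. The design effect is 1 + 29 × ICC, which is 1.58 or 2.45, so the effective sample size is 60/1.58 = 38.0 or 60/2.45 = 24.5. The exact limit at an observed 65%, using that effective size, is 47.8% or 43.3%, so 39/60 no longer passes. The threshold rises to 41 or 43. With a beta-binomial count in each clinic:

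| True rate | ICC 0.02 (at least 41) | ICC 0.05 (at least 43) |
|---|---|---|
| 65% | 0.38 | 0.28 |
| 70% | 0.64 | 0.48 |
| 75% | 0.86 | 0.70 |

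The threshold has to move with the ICC. Keeping it at 39 would pair a clustered count with an interval that assumes independence.

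**The case against.** The strongest reply is that 9.2 is a precision statement and its numbers are right. It opens with the aim of a reasonably precise estimate, makes the limits conditional on an assumed 65% to 75%, and claims no power. Justifying a pilot by expected interval width is ordinary practice. This stands in part: the limits contain no arithmetic error, and anyone who infers one from this point would be mistaken. It does not cover the further step of saying that the limit will not drop below 50%, which is a claim about the trial's result.

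A second reply is that this is a pilot. Section 1.1 does say "though this pilot study is not designed [or powered] to detect a statistically significant change", but that remark concerns the change in TSDD, not the feasibility target by which 9.2 justifies N.

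A third is that 56% applies only at the bottom of the range. That is true. At the midpoint the chance is 84%, and averaged evenly over 65% to 75% it is about 81%.

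A fourth is that the target might mean an observed proportion of 50%. Then 30/60 would suffice, and the chance at 65% would be 99.4%. The wording of 9.2 goes through the lower limit, so that reading is less natural, but a gap from 56% to 99% is a reason to state the rule explicitly.

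A reader might also infer that an intervention performing as assumed would be stopped almost half the time. The documents do not support this. Section 9.2 says that meeting the target allows progression and does not say what follows a miss; section 9.3 plans no interim analyses and sets out no stopping rule.

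**Conclusion.** The point holds as a misdescribed property of the design. The two limits are correct for observed results of 39/60 and 45/60, but the claim that the lower limit stays at or above 50% across the assumed range is not a property the design has at the low end. The chance of meeting the criterion is about 56% there and reaches 80% only from a true rate of about 69%.

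These figures rest on the two-sided exact interval inferred from the plan's own numbers, N of exactly 60, independent patients, and the lower-limit reading of the target. With other common two-sided intervals the figure at 65% is about 66%, which leaves the conclusion unchanged. A cluster-adjusted interval makes the position worse at every rate in the range: about 38% to 28% at a true 65% for an assumed ICC of 0.02 to 0.05.

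**What to change.** In section 9.2:

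1. Name the interval as two-sided 95% exact (Clopper-Pearson).
2. State the progression criterion as a lower 95% limit of at least 50%. Note that this means 39 or more if N is exactly 60, and that the count is to be recomputed for the number actually enrolled.
3. Say that 51.6% and 62.1% are the limits if the observed proportion is 65% or 75%.
4. Replace the statement that the limit will not drop below 50% with the probability of meeting the criterion: about 56%, 84% and 97% at true rates of 65%, 70% and 75%, and 80% only from about 69%. Label these as ignoring clustering in two clinics.
5. If the interval is to be adjusted for clustering, say so, state the assumed ICC, and give the lower probabilities that follow with the adjusted threshold.

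The cost is wording in one section and a less favourable stated figure. It needs no extra patients and no change to conduct or data collection. Only item 5, if adopted, would change the planned analysis.

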on input from successive rounds of focus groups and then administered by mail through the clinic. There is no direct interaction between the study team and PLWD

- *Randomization, blinding and any stratification*

There is no patient-level randomization. Within each health system (University of Michigan and Henry Ford), we will randomly select one of the clinics where patients will receive the nudge intervention.

- *Other protocol specific details, such as centralization of evaluations (e.g., central laboratory or central reading center for clinical scans).*

n/a

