9.2.1 Treatment Assignment Procedures

We will randomly select one clinic (or more, as needed to meet the target sample size) within Michigan Medicine and Henry Ford Health System as the intervention clinic; PLWD in these clinics will receive the nudge intervention. PLWD within the other clinic in each system will serve as controls.

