9.5 Data Analyses

- **Aim 1** will involve rapid and rigorous qualitative analysis. Focus group discussions and any follow-up phone calls will be audio recorded. Following transcription of focus groups, the transcripts will be used to create summaries for each focus group, which will then be reconciled through discussion. Summary data regarding tool refinement and recipient engagement will be transferred into a matrix for interpretation and comparison across groups. This matrix will be reviewed by all pilot investigators to select final refinements of the tool as well as to finalize the Aim 2 engagement strategy. If participants selected for a follow-up phone call agree to being recorded, the brief discussion will be audio recorded for accuracy purposes.
- **Aim 2:** With **N=120** PLWD, we expect to obtain a reasonably precise estimate of the first feasibility outcome, allowing us to determine the number of clinics within each health care system needed for the future ePCT.
- **Aim 3:** Four months after sending the tool, we will do a final EHR query (**Aim 3**) for all participants to assess the burden of CNS polyRx (i.e., total standardized daily dosage) and determine whether the prescribing regimen changed from the medications prescribed at baseline. We will use each active outpatient prescription for a CNS-active medication and convert them to a standardized daily dose using the minimal effective geriatric daily dose, adding the total across all CNS-active medications at the patient level. This—change in the total standardized daily dosage (TSDD) following the nudge intervention—will be the primary outcome for the study and subsequent trial. With the expected sample size of 120 PLWD (60 per group and 30 per clinic-group), we expect to have a good estimate of the variability of the distribution of change in TSSD (clinical outcome

measure) from baseline in each group as well as within-clinic correlation of the changes in TSSD.

Data analysis will be completed by a [name] team analyst, under supervision of the study biostatistician. Because the nature of the intervention is that any changes are made by the PLWD in consultation with their treating clinician, there are not trial results or information to provide to the clinician at completion of the pilot study (i.e., the intervention does not entail treatment changes other than those made by the treating clinician).

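### The feasibility lower limits of 51.6% and 62.1% in Section 9.2 treat 60 patients from two clinics as independent, so they are too favourable as support for the 50% gate to a multi-clinic trial if within-clinic correlation is positive

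*Combined protocol and SAP*

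**What the plan says.** Section 9.2 sets a feasibility target on the proportion of patients with a documented discussion of their CNS-active medications. The lower 95% limit is "not to drop below the pre-determined target of 50" per cent. The calculation is made "With N=60 PLWD (i.e., the PLWD in the intervention clinics"), at assumed proportions of 65% and 75%, and gives lower limits for the "feasibility target will be 51.6% to 62.1%, respectively". The interval method is not named. The section then gives the result a decision role: "Meeting the implementation feasibility target will allow us to proceed to a full ePCT". It also says the estimate will inform how many clinics the future trial needs in each health system.

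Allocation is by clinic. Section 3 (randomization) says that within each health system "we will randomly select one of the clinics where patients will receive the nudge intervention", and Section 9.2.1 allows "one clinic (or more, as needed to meet the target sample size"). Section 9.2 gives 60 patients across two intervention clinics, and Section 9.5 gives 30 per clinic. Within-clinic correlation appears once, in Section 9.5 under Aim 3, which expects to estimate the variability of the clinical outcome "as well as within-clinic correlation of the changes in TSSD". Nothing comparable is said about documented discussion.

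**The concern.** A binomial limit on 60 patients assumes that one patient's outcome says nothing about another's in the same clinic. Here the outcome is a note made by a prescribing clinician or pharmacist, and patients of one clinic share those staff. Section 6.2.4 lists possible barriers, such as access to clinical pharmacists and psychosocial resources, that could differ between clinics. The plan accepts that correlation is possible for change in total standardized daily dosage (TSDD), but not for the outcome that gates the next trial.

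If the only question were the rate in these two clinics, the binomial limit would do. Section 9.2 asks more of it: it supports a decision to proceed to a larger trial in other clinics, and the number of clinics for that trial. For those uses, differences between clinics are part of the uncertainty. Leaving them out makes the limits look better than they are and raises the chance of proceeding when the wider rate is only 50%.

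**Working it through.** **Inputs.** 60 patients, two intervention clinics and planning proportions of 65% and 75% (Section 9.2); 30 per clinic (Section 9.5). The ICC is an assumption, because the documents give no value for any outcome. The range 0.01 to 0.10 is used for illustration.

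**Step 1: reproduce the stated limits.** The two-sided 95% exact (Clopper-Pearson) lower limit is the 0.025 quantile of Beta(x, n − x + 1).
- 65%: x = 39, n = 60, limit 51.60%
- 75%: x = 45, n = 60, limit 62.14%

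Both match. Other methods do not match both figures: for example, Wald gives 52.9% and 64.0%, Wilson 52.4% and 62.8%, and one-sided exact 53.6% and 64.2%. So the stated figures contain no allowance for clustering.

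**Step 2: the pass mark.** If the gate is read as a lower limit not below 50%, 39/60 passes (51.6%) and 38/60 does not (49.9%). The lower planning value of 65% is therefore the smallest count that passes.

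**Step 3: adjusted limits.** Design effect = 1 + (30 − 1) × ICC; effective n = 60 / design effect. The limit is then recalculated with the effective n in place of n and x = p × effective n. For example, at ICC 0.02 the design effect is 1 + 29 × 0.02 = 1.58 and the effective n is 60/1.58 = 38.0.

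| Assumed ICC | Design effect | Effective n | Exact limit at 65% / 75% | Wilson limit at 65% / 75% |
|---|---|---|---|---|
| 0 | 1.00 | 60.0 | 51.6 / 62.1% | 52.4 / 62.8% |
| 0.01 | 1.29 | 46.5 | 49.6 / 60.1% | 50.6 / 61.0% |
| 0.02 | 1.58 | 38.0 | 47.8 / 58.3% | 49.1 / 59.4% |
| 0.05 | 2.45 | 24.5 | 43.3 / 53.5% | 45.3 / 55.3% |
| 0.10 | 3.90 | 15.4 | 37.2 / 47.0% | 40.5 / 50.0% |

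The exact limit reaches 50% at an ICC of about 0.008 for 65% and about 0.076 for 75%. With Wilson limits the crossings are about 0.014 and 0.100.

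**Step 4: chance of passing.** The total is modelled as the sum of two independent beta-binomial counts of size 30 with the given ICC, and passing means 39 or more.

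| Assumed ICC | True 50% | True 65% | True 75% |
|---|---|---|---|
| 0 | 1.4% | 55.9% | 97.0% |
| 0.01 | 2.6% | 55.5% | 95.1% |
| 0.02 | 4.0% | 55.2% | 93.2% |
| 0.05 | 8.2% | 54.7% | 88.6% |
| 0.10 | 13.8% | 54.4% | 83.4% |

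**Step 5: if clinics are added.** With, for example, four intervention clinics of 15, the design effect is 1 + 14 × ICC. The chance of passing at a true 50% is then 1.9%, 2.6%, 4.6% and 7.9% at ICC 0.01, 0.02, 0.05 and 0.10. The effect shrinks but remains.

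**The case against.** The strongest reply is that the limits contain no error: they are right for the two clinics, this is a pilot, and the size of the problem rests on ICC values the documents do not supply. The first part stands. A reader might infer that 51.6% and 62.1% were miscalculated; Step 1 shows that they were not. Nor does correlation bias the observed proportion when clinics are of equal size. But a missing ICC is a reason to state the assumption and show a range. The disclaimer in Section 1.1 about power concerns the change in TSDD, not this proportion, which has its own precision claim and its own decision role.

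A second tempting reading is that clustering makes the 65% case precarious. It does lower the limit there. But the chance of passing at a true 65% is about 54–56% whatever the ICC, because 39/60 is the smallest passing count. Clustering acts mainly on the chance of passing at a true 50%, and more modestly at 75%.

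A third point is method. An exact limit applied to a fractional effective n is conservative, and Wilson limits are about 1 to 3 points higher. At ICC 0.01 and 65%, exact gives 49.6% and Wilson 50.6%. For that reason the adjusted limits should not be turned into a new required count.

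Finally, Section 9.2 calls the 50% target predetermined, so the limits illustrate precision and do not derive the target. Its wording on proceeding is permissive, and the lower-limit rule is a reasonable reading of it but not the only one.

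**Conclusion.** The point holds as an unstated assumption, not as an arithmetic error. The limits are valid for 60 independent patients and describe the two participating clinics. For deciding on and sizing a multi-clinic trial they are too favourable at any positive ICC. Over an assumed ICC of 0.01 to 0.10, the exact limit drops by 2.0 to 14.4 points at 65% (51.6% to between 49.6% and 37.2%) and by 2.0 to 15.1 points at 75% (62.1% to between 60.1% and 47.0%). On the 39/60 reading, the chance of passing at a true 50% rises from 1.4% to between 2.6% and 13.8%.

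This rests on two clinics of 30, a common ICC, and the assumed ICC range. The documents do not support naming one ICC above which the decision is compromised, and nothing here shows that the target would be missed. The 75% case keeps a limit above 50% at ICC 0.05, though not at 0.10 with the exact method. The matter should be fixed, but the remedy is modest.

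**What to change.** In Section 9.2:

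1. Label 51.6% and 62.1% as exact limits that assume independent patients and apply to the participating intervention clinics.
2. Beside them, give the limits adjusted by 1 + 29 × ICC over a stated, assumed ICC range such as that in Step 3. Recalculate from actual clinic sizes if clinics are added under Section 9.2.1.
3. State that two intervention clinics, one per health system, cannot estimate this ICC reliably: pooled, they give one degree of freedom, and clinic is confounded with system.
4. Report the per-clinic proportions, as description, when judging the 50% target.

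The cost is protocol wording and a small table, with no added patients, clinics or data collection. The downside is that the stated limits become less favourable.

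A separate editorial correction does not depend on the ICC. Section 9.5 (Aim 2) says of N=120 that "we expect to obtain a reasonably precise estimate of the first feasibility outcome", and the opening of Section 9.2 attaches the same claim to the total of 120, although the limits use 60. Both should say that N=60 supports this estimate. Section 3 says that all 120 receive the intervention, which conflicts with its own two control clinics; it should say about 60 of the 120.
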